10	09/27/2021	Switched [name] and [name]'s roles on study team, making [name] the new PI; updated consent forms/information sheets and surveys to indicate [name] as the PI; added DDCC Community Outreach and Engagement team member [name] to research study team; removed research study coordinator phone number from 3 and 6 month follow-up surveys to correspond with telephone number removal approved in modification 7 (leaving email as the method by which participants can contact the study coordinator)	Yes
11	04/12/2022	Added new team member, [name] to protocol and removed [name], who resigned from program.	No
12	09/14/2022	Removal of some names; replacing with title/role only. Rebranding. Correction of age range for the study as noted in Revision 9.	NO
13	9/28/2022	Added details about in-person recruiting at community events for web-based module. See page 25.	
14	10/6/2022	Per the request from the IRB, we have clarified that in person	
15.	09/25/2025	To be in compliance with outcomes reporting requirements for clinicaltrials.gov, this revision is being submitted to update the protocol to reflect the work that was accomplished. Many aims and outcome measures had to be curtailed because of delays and constraints relating to the COVID-19 pandemic. This revision is a simplification of the original aims and reflects the work that was conducted, removing aims	

PROTOCOL TITLE: *Screen to Save 2*

		and hypotheses that could not be completed. The protocol is greatly simplified, consisting of one intervention with pre- and post- surveys.	
--	--	---	--

Table of Contents

1.0	Study Summary.....	8
2.0	Objectives*	10
3.0	Background*	10
4.0	Study Endpoints*	11
5.0	Study Intervention/Investigational Agent	11
6.0	Procedures Involved*	12
7.0	Data and Specimen Banking*	14
8.0	Sharing of Results with Subjects*	14
9.0	Study Timelines*	15
10.0	Inclusion and Exclusion Criteria*	15
11.0	Vulnerable Populations*	16
12.0	Local Number of Subjects	17
13.0	Recruitment Methods.....	17
14.0	Withdrawal of Subjects*	18
15.0	Risks to Subjects*	19
16.0	Potential Benefits to Subjects*	20
17.0	Data Management* and Confidentiality	20
18.0	Provisions to Monitor the Data to Ensure the Safety of Subjects*	22
19.0	Provisions to Protect the Privacy Interests of Subjects.....	22
20.0	Compensation for Research-Related Injury.....	23
21.0	Economic Burden to Subjects	23
22.0	Consent Process	23
23.0	Process to Document Consent in Writing	25
24.0	Setting	25

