1.0 Study Summary

Study Title	Screen to Save 2
Study Design	Prospective Observational/Cohort Study Pre-/Post-/Follow-up (via surveys)
Primary Objective	Implement and evaluate Screen to Save (S2S) outreach and educational activities to improve knowledge of colorectal cancer screening methods, to increase intent to get screened for colorectal cancer, and connect screening services to 45-74 year-old residents living in NH and VT—focusing on the most rural counties (RUCC 7—9).
Research Intervention(s)	Education about colorectal cancer screening via online video and written education materials.
Study Population	
The target population is adults aged 45-74 years old who reside in rural New Hampshire or Vermont; “rural” = Rural Urban Continuum Codes (RUCC) 7—9 counties (Coos and Sullivan County, NH; Caledonia, Windsor, Windham, Orange, Orleans, Lamoille, and Essex County, VT)
 
To be eligible to enroll in the study, people must meet the following eligibility criteria:
 
-Be a resident of one of the RUCC 7—9 counties in NH and VT and-Be 45-74 years-old at the time of enrollment 
except in the instance of recruitment via Experimental Arm 4 (e.g. recruitment through Little Rivers Health Care, Inc.), in which case individuals may enroll in the study if age 45-74 and if residing in states or counties other than those specified above, if agreed upon by the research study team and partner institution

Sample Size	Our target recruitment size is 196-225 participants completing the pre/post survey in each of two arms (Arms 2 and 4). Recruitment into study arm 3 will be discontinued in April 2021 due to changes in lung cancer screening guidelines affecting the educational intervention content, resulting in fewer than 196 participants completing that arm. Projecting that up to 50% of people who consent may not complete the pre/post survey, we project that up to 950 people may be enrolled total.
Study Duration for individual participants	Up to 7.5 months
Study Specific Abbreviations/Definitions	S2S= Screen to Save CRC= Colorectal Cancer LCS= Lung Cancer Screening NCI= National Cancer Institute CRCHD=Center to Reduce Cancer Health Disparities (a division of the National Cancer Institute) NON= National Outreach Network (an effort of CRCHD) CHE= Community Health Educator

PROTOCOL TITLE: *Screen to Save 2*

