4.0 Study Endpoints*

4.1. Knowledge, attitudes, and behavioral intentions related to colorectal cancer risk factors, screening, and prevention (assessed via pre/post/follow-up surveys)

4.2 Uptake of colorectal cancer screening (behavior change) as a result of the outreach models (assessed via follow-up survey)

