6.0 Procedures Involved*

6.1—6.5. This study uses a pre/post/follow-up design utilizing surveys. See below for more information about the surveys.

Our CHE will use a web-based educational-format with video and accompanying educational information shared through social media outreach to conduct a similar intervention as described in experimental arm 1. Recruitment will be facilitated through paid advertisements in Facebook, which will be targeted to 4574 year-old residents in RUCC 7, 8, and 9 counties throughout VT and NH. The advertisements will ask the prospective participants to click to 'learn more' and will be directed to a Qualtrics survey, which will lead them through:

- a- A consenting process utilizing the research information sheet (see enclosed information sheet and waiver of signature).
- b- Screening for eligibility- Prospective participants will be asked a) to select the age group that they are part of; b) Which state they live in; and c) Which county they live in. Participants indicating that they are between the ages of 45—74 years old and live in one of the nine RUCC 7—9 counties in NH and VT will be eligible. Prospective participants will be required to answer the eligibility screening questions in order to advance to the remainder of the study content: the rest of the survey and educational intervention. Participants who do not meet eligibility criteria will be informed that they do not meet the eligibility criteria.
- c- A pre-test survey - Answering pre-test and post-test knowledge questions about colorectal cancer and screening and colorectal cancer behavior intentions questions will be required in order for participants to progress through the study, as will answering a question about the participant's age in years. Answering all other demographic questions and questions about

PROTOCOL TITLE: *Screen to Save 2*

personal or family health experiences will either be required with a “decline to answer” option or optional. Some online questions (i.e. lung cancer and colorectal cancer knowledge questions) will be presented in a random order using Qualtrics features for randomization.

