17.0 Data Management* and Confidentiality

17.1. Our sample size is based on a two-tailed test with 0.05 significance level, and 80% power to detect an effect size of 0.2 (20% difference in the before/after difference-in-difference estimates), with a standard deviation of 1.0. We will conduct various statistical tests on the data to determine whether participants experienced changes in knowledge, attitudes, behavioral intentions, and behavior as a result of the intervention, and changes will be look at across groups.

17.2. To ensure confidentiality of data, we will have several safeguards in place:

- Training: All research team members with access to study data will be trained on all procedures related to data management under this protocol.
- Access restrictions: Access to electronic research materials/data will be limited to those on the research team. This will include only granting electronic access to Qualtrics and One Drive/Sharepoint to study team

PROTOCOL TITLE: *Screen to Save 2*

members, these sites/applications also require passwords to access. All laptops/computers being used will also be encrypted and password-protected. Access to physical research materials/data will also be limited by being stored in locked filing cabinets at DHMC.

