22.0 Consent Process

Once the prospective participant clicks the Facebook ad to learn more about the study and answers the initial eligibility screening questions, the prospective participant will be presented with an information sheet (attached) and asked to read it before proceeding. As part of the information sheet, participants will be provided with contact information for the study team should they have any questions before proceeding. Once they initial and click the arrow button to

PROTOCOL TITLE: *Screen to Save 2*

provide implicit consent to participate in the study, they will be asked to complete the following components (in the same session):

- eligibility screening questions (participants not meeting eligibility age and geographic criteria will have their study participation end at that point; eligible participants will be able to advance to the next sections),
- pre-test with added tobacco and lung cancer screening questions
- educational module,
- tailored education/information about talking with a healthcare provider, local healthcare providers, and local insurance/benefits resources
- Post-test questions pertaining to cancer screening/prevention—including lung cancer screening—and other health behavior intentions,
- study participant providing name and contact information, and
- information about e-gift card distribution.

We will be following procedures outlined in HRP-090, with a few exceptions:

- Section 3 of HRP-090:
 - 3.8- If the prospective participant expresses interest in participating, based on clicking on the social media ad, the participant will then be invited to review an information sheet and continue into the study, if they are interested. They will also be provided with study team contact information, should they have questions before consenting to participate.
- Section 5 of HRP-090:
 - 5.3- An information sheet will be presented to the participants. See enclosed information sheet.
 - 5.4 and 5.5- Participants will be provided with study team contact information, should they have questions or want to talk with family/friends before consenting to participate.
 - 5.7- Participants will be completing an implicit consent process, which is explained in the information sheet. We will have participants read and confirm the following:

Please confirm that you have done each of the following (by checking each box):

_ I have read the above information about this study.

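### Section 17.1 bases power on a difference-in-difference and attributes change to the intervention, but the current protocol describes one intervention and no comparator

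*Combined protocol and SAP*

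**What the plan says.** Section 17.1 bases the sample size on a two-tailed 0.05 test with "80% power to detect an effect size of 0.2 (20% difference in the before/after difference-in-difference estimates), with a standard deviation of 1.0". It then promises various tests of "changes in knowledge, attitudes, behavioral intentions, and behavior as a result of the intervention, and changes will be look at across groups". The groups are not named. Section 4.2 lists as an endpoint "Uptake of colorectal cancer screening (behavior change) as a result of the outreach models (assessed via follow-up survey").

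The design described elsewhere is a single cohort. The Section 1.0 design entry reads "Prospective Observational/Cohort Study Pre-/Post-/Follow-up (via surveys"), and Section 6.0 opens with "This study uses a pre/post/follow-up design utilizing surveys". Section 5.0 describes one web-based module. Revision 15 in the revision history, which describes the current version, says: "The protocol is greatly simplified, consisting of one intervention with pre- and post- surveys". Under Section 22.0, once participants consent, "they will be asked to complete the following components (in the same session"); the list runs from pre-test through education to post-test questions.

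Remnants of a multi-arm design remain. Section 1.0 sets a target of "196-225 participants completing the pre/post survey in each of two arms (Arms 2 and 4"), while Section 12.0 gives 196-225 completers and names no arms. Sections 10.3 and 17.4 mention a control arm in passing. In Section 1.0, Arm 4 differs by its route of recruitment (a healthcare partner) and by a relaxed residence rule.

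**The concern.** A difference-in-difference compares change in one group with change in another. No section describes a second condition, how people would be allocated to it, or a between-group hypothesis. The only power statement therefore refers to a contrast that the plan does not define.

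Three things are at stake. First, the claim of 80% power may be read as covering a group comparison, for which the targets may give much less. Second, because the groups are unnamed, the comparison could be chosen after the data are seen. Third, attributing change to the intervention goes beyond what a before-after change in one cohort can show. For knowledge, answering the same items twice in one session cannot be separated from learning. For uptake over three to six months, nothing stands in for the screening that would have happened anyway.

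**Working it through.** **Inputs.** From Section 17.1: two-sided alpha 0.05 (z = 1.960), power 80% (z = 0.8416), effect 0.2, SD 1.0. From Sections 1.0 and 12.0: 196-225 completers. The documents give neither the pre/post correlation r nor an allocation ratio. Values of r below are assumptions, and equal arms are assumed for the two-group case.

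**Step 1. Reproduce 196 as a paired mean change, taking 1.0 as the SD of change.**
n = ((1.960 + 0.8416) × 1.0 / 0.2)² = 14.008² = 196.2. The exact paired t-test gives 199.
Power = Φ(0.2√n − 1.960):
- n = 196: Φ(2.80 − 1.96) = 80.0% (79.6% by paired t)
- n = 225: Φ(3.00 − 1.96) = 85.1% (84.8% by paired t)

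**Step 2. The same inputs as a two-group difference in change.**
n per arm = 2 × 196.2 = 392.4, so 393.
Power = Φ(0.2√(n/2) − 1.960):
- 196 per arm: Φ(1.980 − 1.960) = 50.8%
- 225 per arm: Φ(2.121 − 1.960) = 56.4%

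The smallest difference detectable with 80% power is 2.8016 × √(2/n), which is 0.283 at 196 per arm and 0.264 at 225 per arm.

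Reading the 20% as a difference of 20 percentage points, from assumed starting rates of 20-50%, gives 82-97 per group. That does not reproduce 196 either.

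**Step 3. What if 1.0 is the SD of a single score?**
The SD of change is then √(2(1 − r)), and each sample size above is multiplied by 2(1 − r).

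| r (assumed) | SD of change | Paired n | Paired power at 196 | Two-group n per arm | Two-group power at 196 / 225 per arm |
|---|---|---|---|---|---|
| 0.3 | 1.183 | 275 | 66% | 550 | 39% / 43% |
| 0.5 | 1.000 | 197 | 80% | 393 | 51% / 56% |
| 0.7 | 0.775 | 118 | 95% | 236 | 72% / 78% |

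Two-group power reaches 80% at 196 per arm when 392.4 × 2(1 − r) = 196, that is, r = 1 − 196/784.8 = 0.75.

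**Step 4. Targets.** Section 1.0 implies 2 × 196 = 392 to 2 × 225 = 450 completers over Arms 2 and 4. Section 12.0 gives 196-225.

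**Step 5. Attribution.** Arms 2 and 4 are the only arms with a current target. Section 1.0 separates them by recruitment route and residence rule, so a difference between them would not isolate the education. The bias from retesting or background screening cannot be sized, because the documents give no figure for either.

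**The case against.** The strongest reply is that 17.1 does not say which SD 1.0 is. If it is a single-score SD and r is about 0.75, a two-group comparison at 196 per arm does have 80% power. This stands, and any statement about low two-group power must be conditional on the SD and r. It applies equally to the paired reading, whose power at 196 runs from about 66% to 95% as r goes from 0.3 to 0.7.

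Second, the paired origin of 196 is inferred from arithmetic. A two-group requirement of 393 mistaken for a total and split in two would give 196.5 per arm, the same figure. This also stands. A reader might infer that the sponsor performed a paired calculation and mislabelled it; the documents do not show that.

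Third, Revision 15 was filed to reflect work already done, so silently replacing the sample-size basis would rewrite the record, and deleting the group wording could remove an intended Arm 2 versus Arm 4 comparison. This is fair. The remedy should mark the old basis as superseded and let the sponsor choose between naming the groups and stating that there is no comparison.

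Fourth, an aim or hypothesis may express a hoped-for effect, and Section 3.3 is background. Agreed: the wording that matters is in the analysis text and the endpoint, 17.1 and 4.2. Within these, same-session knowledge change is less exposed to outside trends than uptake over months, though retest effects remain.

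The reply that this is merely leftover wording does not succeed. No other section states the analysis, so this wording is the operative plan.

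**Conclusion.** The point holds. As written, 17.1 claims 80% power for a between-group contrast that the current design does not contain, and 17.1 and 4.2 attribute change in a way a single cohort cannot support. If 1.0 is the SD of change, 196-225 gives 80-85% power for a paired change of 0.2. A two-group difference in change needs 393 per arm and has about 51-56% power at 196-225 per arm. Under a single-score SD, both depend on r, which is not stated. The conflict between 392-450 and 196-225 completers holds under any reading of the SD.

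Two stronger inferences are not supported. One is that the study is certainly underpowered for a group comparison: that depends on the unstated SD and r. The other is that an undisclosed control arm is to be analysed: the mentions in 10.3 and 17.4 come with no content, allocation or hypothesis, and read as remnants to be reconciled. Nor does the point imply that the education has no effect; it says only that this design cannot separate its effect from retesting or background screening.

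The sponsor should make this change, but it is a matter of wording and analysis definition in a minimal-risk study.

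**What to change.** 1. **Sample-size basis (17.1).** Replace the difference-in-difference basis with power for a within-person pre/post change of 0.2. State which SD 1.0 represents, the outcome it applies to and, if it is a single-score SD, the assumed r and the resulting power. Mark the difference-in-difference basis as superseded rather than erasing it, and give precision (95% CI) at the achieved number of completers.
2. **Groups and targets.** Either state that no between-group comparison is made and remove the reference to groups, or name them (for example, Arm 2 versus Arm 4) and label the comparison non-randomised, descriptive and not powered at 80% unless the SD and r are shown to support it. Reconcile the target in Section 1.0 with Section 12.0, and the control-arm mentions in 10.3 and 17.4 with the current design.
3. **Attribution (17.1 and 4.2).** Use before-after wording. Analyse knowledge as mean paired change with a 95% CI. Analyse intention in unscreened adults, as hypothesis 2.2(b) states, with a paired method. Report uptake as a descriptive proportion with a 95% CI among those followed up, without crediting it to the education.

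No new data are needed. The cost is that the causal wording, and the claim of power for a group comparison, are given up.

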18.0 Provisions to Monitor the Data to Ensure the Safety of Subjects*
N/A- This study involves only minimal risks.

19.0 Provisions to Protect the Privacy Interests of Subjects

Contact information requested from participants for purposes of follow-up and gift card distribution will be obtained at the time of the first (pre/post) survey in Qualtrics. When the data are converted to a data file for analysis, a study team member will assign and add a six-digit NCI code to each participant's responses or a shortened version of that code and upon doing so that study team member will remove the participant's name and contact information from that data file used for analysis. Separate documents will be created containing the participant name, contact information, and code for follow-up and gift card distribution. As noted in section 17 of this protocol, within the online Qualtrics platform there may be a way to link the three and six-month follow-up surveys back to

PROTOCOL TITLE: *Screen to Save 2*

participants' first surveys where their names and contact information are provided; however, three- and six-month files used for data analysis will not contain participants' names or contact information, only their assigned NCI numbers or shorted versions of those numbers and the month of their original participation. Only study team members will have access to the Qualtrics online platform and the data analysis files produced from Qualtrics via the password protected systems and encrypted devices as noted in section 17.2 of this protocol.

The default method for completing the follow-up survey will be through the internet at a time/place of the participants' choosing. Should any participants choose to complete the survey by phone with a CITI trained research team member, the research team member will take steps to ensure that others are not able to overhear the phone call (e.g., closing door, not using speaker phone).

19.3 Only study team members will have access to forms containing identifiable information. This information will only be accessed for relevant study purposes such as gift card distribution, follow-up survey administration, and checking online survey data collected for authenticity to protect against including automated online responses (bots) and duplicate participation.

20.0 Compensation for Research-Related Injury

This study involves no more than minimal risk to subjects.

21.0 Economic Burden to Subjects

Study participants will not be subject to any costs for participating in the study/educational interventions.

Should our intervention be effective in encouraging them to get screened for colorectal cancer, all costs associated with screening and/or visiting a healthcare professional to discuss screening will be the participants' responsibility.

22.0 Consent Process

Once the prospective participant clicks the Facebook ad to learn more about the study and answers the initial eligibility screening questions, the prospective participant will be presented with an information sheet (attached) and asked to read it before proceeding. As part of the information sheet, participants will be provided with contact information for the study team should they have any questions before proceeding. Once they initial and click the arrow button to

PROTOCOL TITLE: *Screen to Save 2*

provide implicit consent to participate in the study, they will be asked to complete the following components (in the same session):

- eligibility screening questions (participants not meeting eligibility age and geographic criteria will have their study participation end at that point; eligible participants will be able to advance to the next sections),
- pre-test with added tobacco and lung cancer screening questions
- educational module,
- tailored education/information about talking with a healthcare provider, local healthcare providers, and local insurance/benefits resources
- Post-test questions pertaining to cancer screening/prevention—including lung cancer screening—and other health behavior intentions,
- study participant providing name and contact information, and
- information about e-gift card distribution.

We will be following procedures outlined in HRP-090, with a few exceptions:

- Section 3 of HRP-090:
 - 3.8- If the prospective participant expresses interest in participating, based on clicking on the social media ad, the participant will then be invited to review an information sheet and continue into the study, if they are interested. They will also be provided with study team contact information, should they have questions before consenting to participate.
- Section 5 of HRP-090:
 - 5.3- An information sheet will be presented to the participants. See enclosed information sheet.
 - 5.4 and 5.5- Participants will be provided with study team contact information, should they have questions or want to talk with family/friends before consenting to participate.
 - 5.7- Participants will be completing an implicit consent process, which is explained in the information sheet. We will have participants read and confirm the following:

Please confirm that you have done each of the following (by checking each box):

_ I have read the above information about this study.
_ I understand that I can contact the study team using the contact information provided, should I have any questions about the study.
_ I understand that participating in this research study is completely voluntarily and that I can stop participating at any time.

Clicking the button at the bottom of the screen to continue forward indicates your consent to participate in this study.

PROTOCOL TITLE: *Screen to Save 2*

Non-English Speaking Subjects: At this time, we will not enroll non-English speaking subjects.

Subjects who are not yet adults: We will not enroll any subjects who are not yet adults. Our age requirements are 45-74 years old at the time of enrollment. Anyone outside of this age range will be screened-out of participating.

Adults unable to consent and cognitively-impaired adults: We do not intend to enroll adults who are unable to consent or cognitively-impaired adults. For online participants, there are several steps involved in accessing our study which, we feel, will safeguard against these populations participating in the study; for example, in order to access the study online, that will require having a social media account, navigating away from the social media account to our survey site, reading the information sheet, and proceeding forward to the survey.

